Component 3: Self-Management Tools. Families will be provided with psychoeducational tools in English or Spanish through the Nemours App to promote lifestyle behavior change. These will include a self-monitoring tool (Figure 3) to track daily progress toward lifestyle behavior goals established during visits, a series of culturally-relevant videos developed by the research team to promote positive parenting among families of children with obesity (see A.3, Figure 4), and media-based educational resources (e.g., exercise/ cooking videos) to promote healthy lifestyle behaviors curated by multidisciplinary obesity specialists. Obesity specialists and community health workers will review data on an EHR dashboard about lifestyle behavior goal metrics and anthropometric measurements to inform clinical decisions during visits with families. Participants will also have the option of accessing the YMCA of Delaware's virtual platform through the App at no cost to participants.

Figure 4. Positive Parenting Videos

Figure 3. Goal Tracking

C.4 STUDY DESIGN: See PHS Human Subjects & Clinical Trials form for detailed eligibility criteria, sample size justification, recruitment/retention plan, time-line, human subjects protection, and data/safety monitoring. All participating

families will receive compensation for study visits, as detailed on the form.

AIM 1. REFINE MICCO WITH COMMUNITY ENGAGEMENT AND THINK ALOUD TESTING

COMMUNITY ENGAGEMENT

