
AIMS 2 and 3: EXAMINE IMPACT OF MICCO ON FAMILY ENGAGEMENT AND CHILD ADIPOSITY AND DISPARITIES IN THESE OUTCOMES

PARTICIPANTS: 184 families of children with obesity (BMI percentile $\geq 95^{\text{th}}$ percentile for age) ages 4-12 years who are patients of the primary care practices in Milford, Seaford, or Millsboro serving primarily rural populations will be identified from the EHR and with advertisement at community centers. Participants identified from the EHR will be contacted by text and/or e-mail message. Interested participants will be advised to contact a research team member, who will then contact interested families to assess eligibility criteria and interest in participation. If a family is eligible and interested after this contact, the research team member will arrange a time to conduct an informed consent process with the participant, who will sign an electronic consent.

STUDY DESIGN: Enrolled families will be randomly allocated to receive MICCO (see C.3) or an active control condition (standard care) using a 1:1 randomization scheme stratified by race/ethnicity (three groups impacted most by obesity in the community: Latino, non-Hispanic Black, non-Hispanic White; Figure 6). The intervention will be delivered over 6 months.

STANDARD CARE: An active control condition was selected to demonstrate the impact of the intervention beyond the typical care that a child would receive in primary care. Standard care will include bimonthly in-person visits for lifestyle counseling with the child's PCP per 2023 AAP Clinical Practice Guidelines.⁴⁷ PCPs will receive training on these recommendations at the start of the clinical trial, with refresher training provided every six months and a lifestyle handout provided to facilitate education at each nursing visit. PCPs will not be trained on MICCO. Only participants in the MICCO group will have access to the MICCO dashboard on the Nemours App to prevent contamination.

OUTCOME MEASURES

Family Engagement in Treatment: Study visits will be documented in the EHR as part of routine clinical care for all patients, including the number of visits with primary care providers (where obesity and lifestyle counseling was provided, per ICD-10 codes) or obesity specialists (including type of specialist) and number of cancelled/missed visits. Attrition (non-attendance to 6 month follow-up visit) will be assessed via EHR review. In addition, number of days in study will be assessed as a secondary outcome.

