Child Adiposity: Weight will be measured with a wireless smart scale that has been used in prior research and demonstrated excellent agreement with research-grade scales.⁴⁹⁻⁵⁰ Height will be measured using a reliable method used by RPL [name] and mentor [name] using a measuring tape and ruler, which has demonstrated validity when compared to measurement of height with a medical-grade stadiometer measured by a research team (Forset, et al., 2022).⁵¹ Procedures for ensuring reliability of measurements using these devices will be followed, per guidelines established by Krukowski and Ross during the pandemic.⁵⁰ Children will be measured by their caregiver each month in advance of visits, with weight measurements transmitted wirelessly to and height measurements entered into the Nemours App for the MICCO Group and measurements entered into the EHR by research staff for the Standard Care group.

Disparities: Child race/ethnicity and insurance (proxy measure of socioeconomic status) will be collected from the EHR. Age, sex, caregiver preferred language, and social needs (from screener) will also be collected.

C5. DATA ANALYTIC PLAN. **Think Aloud Testing (Aim 1):** Themes from qualitative interviews will be identified using an inductive thematic approach (see PHS Human Subjects Form for more detail).⁵³ **RCT (Aim 2):** Based on prior research describing the impact of behavioral interventions on BMI z-scores, we expect a mean difference in adjusted BMI z-score of 0.25 with the intervention, an effect size that has also been associated with a change in cardiometabolic risk.⁸ A sample size of 92 participants (46 in each group) can detect an effect size of this magnitude with a power of 80% and a level of significance of 0.05, assuming a 50% attrition rate based

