on prior studies,¹¹⁻¹² we would need to enroll 184 participants (92 in each group). A mixed effects model with random coefficients will be used to assess the longitudinal effects of MICCO on changes in adjusted BMI z-score to minimize the effect of missing data. Logistic regression analysis will be used to assess the effect of the intervention on attrition. **Disparities (Aim 3):** The same models will be used to preliminarily assess the interaction between the intervention and race/ethnicity and insurance on adjusted BMI z-score and attrition to inform a larger multi-site trial that will be fully powered to evaluate disparities. Due to pilot nature of study and variability in engagement, the decision was made by the COBRE External Advisory Committee to end enrollment after 1 year.

C.6 POTENTIAL PROBLEMS, ALTERNATIVES. Analysis of EHR data suggests that it will be feasible to recruit the sample size intended and advertisement of the study through our community partners will also facilitate recruitment. However, if recruitment is slow we may expand eligibility to include children with BMI $\geq 85\%$ or from other Nemours clinics in rural areas. Every effort will be taken to refine MICCO based on input from stakeholders; if MICCO is found to be ineffective in the RCT, we will obtain qualitative feedback from our Councils, analyze app analytics, and assess whether behavior change improved. We understand that technology evolves quickly and modifications may be needed to ensure that the intervention remains current. We will leverage Nemours' investment in innovative technologies and the expertise of our IMPACT Core to continuously improve our intervention to be state of the art.⁵⁴ If families are experiencing connectivity issues, we may use primary care space and equipment for telehealth visits. Finally, success depends on effective collaboration with the community and therefore we will incorporate metrics to objectively measure collaborative efforts.²⁷

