C.7 SCIENTIFIC RIGOR. This study was designed to ensure that it will yield robust, unbiased results. MICCO incorporates evidence-based strategies for the treatment of childhood obesity that align with USPSTF and AAP guidelines and are informed by the team's preliminary work. Best practice community-engaged research methods and usability testing will be used to tailor and refine the intervention for families of children with obesity in rural communities of Delaware. A RCT will be used to evaluate efficacy of the intervention, with planned sample size calculated to detect a reduction in adjusted BMI z-score that would yield positive cardiometabolic outcomes based on prior research and accounting for attrition rates based on prior studies. Stratified randomization will be used to ensure a diverse and representative sample from which disparities can be preliminarily evaluated. Our study will focus on objective outcome measures to assess intervention efficacy, using innovative and automated technology. We will collect additional information about use of MICCO and components of standard care visits to account for potential variability in participant experience of either intervention. Finally, rigorous data analytic approaches and transparent reporting guidelines will be followed.

C.8 FUTURE DIRECTIONS. This study will position [name] to secure external funding to conduct a large-scale, multi-site implementation trial of MICCO, for example through existing collaborations with the ISPCTN or PEDSnet, leveraging common EPIC interfaces among sites. With a refined intervention and robust data from a single site RCT, [name] will be highly competitive to apply for funding from the NIH (NICHD/NIDDK R01) or funding from PCORI in year 2 of the COBRE, with a larger goal of transforming healthcare delivery and policy for children with obesity to include integrated preventive care and innovative technologies to expand the reach of this care. Importantly, this study will increase capacity for community-engaged research in rural Delaware to ensure that research with these populations continues to be conducted in a meaningful and impactful manner.

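### Randomisation is stratified by race/ethnicity, but the supplied text puts the stratum in neither Aim 2 model; adding it is a minor, almost free improvement if race/ethnicity is prognostic

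*Combined protocol and SAP*

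**What the plan says.** The STUDY DESIGN paragraph under Aims 2 and 3 allocates families "using a 1:1 randomization scheme stratified by race/ethnicity", with three groups. C5 gives each Aim 2 analysis one sentence. For BMI z-score: "A mixed effects model with random coefficients will be used to assess the longitudinal effects of MICCO on changes in adjusted BMI z-score". For attrition: "Logistic regression analysis will be used to assess the effect of the intervention on attrition". Neither sentence names a covariate.

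Race/ethnicity enters a model only under Aim 3, where C5 states: "The same models will be used to preliminarily assess the interaction between the intervention and race/ethnicity and insurance on adjusted BMI z-score and attrition". C.7 explains the stratification by that aim too: "Stratified randomization will be used to ensure a diverse and representative sample from which disparities can be preliminarily evaluated".

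The sample size in C5 is set "with a power of 80% and a level of significance of 0.05, assuming a 50% attrition rate", giving 92 evaluable and 184 enrolled. C5 later records that "the decision was made by the COBRE External Advisory Committee to end enrollment after 1 year", without a final number.

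C.4 sends the reader to a form that was not supplied: "See PHS Human Subjects & Clinical Trials form for detailed eligibility criteria, sample size justification, recruitment/retention plan, time-line". RCT model covariates are not among the items listed there. C5, however, cites the same form for Aim 1 analysis detail, which is not on that list either.

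**The concern.** Stratified allocation balances the arms on the stratum. A model that leaves the stratum out still counts between-stratum variation as noise, so if the stratum is prognostic, the standard error is too large for the design, the test is conservative and some power is lost. The information is already in hand, because child race/ethnicity is taken from the EHR for the disparities aim.

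Two further matters are at stake. With 50% attrition planned for, a BMI z-score model without the stratum can be biased if dropout depends on arm and stratum together. Aim 3 examines that very interaction for attrition, so the plan treats it as open. And an unstated covariate set can be chosen after the data are seen. In the logistic model that choice also changes what the odds ratio means, since an odds ratio conditional on a prognostic stratum lies further from 1 than the marginal one.

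**Working it through.** **1. The plan's own figure.** 46/(1 − 0.5) = 92 per group and 92/(1 − 0.5) = 184 in all, as stated. The 46 per group cannot be reproduced because no SD is given; two-sided at 0.05 it implies SD = 0.25/[2.8016 × √(2/46)] = 0.428. The point does not depend on it.

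**2. Attrition.** From C5: 184 families and 50% attrition, applied here to the control arm. Assumed: 30% attrition on MICCO, strata of 60/62/62, and all stratum rates. The log odds ratio within strata was solved so that overall rates stay at 50% and 30%. There were 20,000 simulated trials per row, analysed by Wald tests.

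| Control attrition by stratum | Power without stratum | With stratum | Gain (points) |
|---|---|---|---|
| equal | 79.4% | 79.8% | 0.4 |
| 45/50/55% | 79.6% | 80.2% | 0.6 |
| 40/50/60% | 79.7% | 81.2% | 1.5 |
| 30/50/70% | 80.0% | 83.1% | 3.1 |

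The 0.4 in the first row arises with no stratum effect, so it is a small-sample feature of the Wald test and not recovered information. The last row implies an odds ratio of (0.7/0.3)/(0.3/0.7) = 5.4 between extreme strata; there the mean log odds ratio is −0.85 without the stratum and −0.96 with it. Type I error without the stratum is 3.4% with exact balance, 3.5% with blocks of 4 or 8, and 4.8% with no blocking (4.9–5.2% with the stratum). The test is thus conservative only if arms are balanced within strata, and no block size is stated.

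**3. BMI z-score change.** Assumed: random intercept (variance 0.25) and slope, residual SD 0.10, seven monthly measures, three equal and evenly spaced strata, and constant monthly dropout leaving 50% at month 6. Calibrating 184 enrolled to 80% power for 0.25 requires SE = 0.25/2.8016 = 0.0892, hence a slope variance of 0.269 per six months. If strata explain a share R² of it, the extreme strata differ in six-month change by 2√(1.5 × R² × 0.269).

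| R² | Extreme strata differ by | Multiple of 0.25 | Power, no stratum | Power, stratum-by-time | Gain (points) |
|---|---|---|---|---|---|
| 2% | 0.18 | 0.7 | 80.2% | 80.7% | 0.5 |
| 5% | 0.28 | 1.1 | 80.5% | 81.7% | 1.2 |
| 10% | 0.40 | 1.6 | 81.1% | 83.5% | 2.4 |
| 20% | 0.57 | 2.3 | 82.3% | 87.1% | 4.8 |

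At 10%, the model without the stratum reports SE 0.0892 while its true sampling SD is 0.0852: Φ[(0.25 − 1.96 × 0.0892)/0.0852] = 81.1%. With stratum-by-time the SE is 0.0852: Φ[0.25/0.0852 − 1.96] = 83.5%. A stratum main effect alone leaves every power figure unchanged. Simulation with REML at 10% gives power of 82.1% and 84.8%, and type I error of 4.3% and 4.9%.

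**4. Bias from dropout by arm and stratum jointly (same model, R² = 10%, treatment effect equal across strata).**

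| Control dropout | MICCO dropout | Bias without stratum | Share of 0.25 |
|---|---|---|---|
| 55/50/45% | 45/50/55% | 0.010 | 4% |
| 60/50/40% | 40/50/60% | 0.020 | 8% |
| 70/50/30% | 30/50/70% | 0.040 | 16% |

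The sign depends on which strata drop out. The mild case is 0.010/0.0892 = 0.11 standard errors. Under these conditions stratum-by-time removes the bias, and dropout by arm alone or by stratum alone causes none.

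That changes if the treatment effect differs by stratum. With effects of 0.15/0.25/0.35 and dropout of 70/50/30% in both arms, the estimate misses the equal-weight average effect by about 0.010 with or without the stratum terms. With effects of 0.05/0.25/0.45, MICCO dropout of 30/50/70% and control dropout of 50% throughout, the miss is about 0.01 with stratum-by-time and about zero without.

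**5. Cost in a small trial.** Assume 80 families in strata of 40/26/14 and no prognostic effect. Logistic power is 45.5% without and 45.6% with the stratum (SE 0.477 and 0.485). Mixed-model power by REML is 45.2% and 44.7% (SE 0.1351 and 0.1355).

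**The case against.** The strongest reply is that this is an omission and not an error. Nothing says the Aim 2 models will be unadjusted, the stratification is justified by Aim 3, where race/ethnicity does enter, and C5 describes the study as a pilot. That stands, and it keeps the point minor.

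The larger gains also need large effects. About 5 points on BMI z-score requires race/ethnicity groups to diverge in six months by 2.3 times the planned treatment effect, and 3 points on attrition requires control rates of 30/50/70%. The documents give no estimate of how prognostic race/ethnicity is for either outcome. That stands too.

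Three stronger readings are tempting, and none is supported.

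- A reader might infer that the stated 80% power is not achieved. In the BMI z-score calculations power without the stratum stays at 80.2% or above, and C5 states no power for attrition.
- A reader might infer that the Aim 2 BMI z-score estimate is biased as planned and that stratum terms cure it. The bias needs a particular dropout pattern together with a prognostic stratum, and the cure is complete only if the treatment effect is equal across strata. Aim 3 leaves that open as well.
- A reader might infer from the C.4 list that the PHS form is silent on the RCT models. Since C5 cites the form for analysis detail that C.4 does not list, the list cannot show this.

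Conversely, the Aim 3 reference to using the same models does not show that the Aim 2 estimates adjust for race/ethnicity.

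**Conclusion.** The point holds as a minor, nearly free improvement. The supplied text stratifies the randomisation by race/ethnicity and does not carry the stratum into either Aim 2 model. If race/ethnicity is prognostic and arms are balanced within strata, the tests are slightly conservative. The power forgone is about 0.4 to 1.5 points under weak to moderate effects, 2.4 points when strata explain 10% of slope variance, and 3 to 5 points only in the strongest cases. If race/ethnicity is not prognostic, nothing is lost by the present wording. Protection against dropout bias is a secondary and conditional benefit.

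Every stratum effect, the 30% MICCO attrition rate, the variance components and the 80-family sample are assumptions. The direction of the conclusion rests on the design; its size rests on those assumptions.

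**What to change.** State in C5 that:

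- the Aim 2 logistic regression includes the randomisation stratum, in the three groups as randomised;
- the Aim 2 random-coefficient model includes stratum and stratum-by-time, since a main effect alone does not alter the precision of the treatment-by-time effect;
- the attrition odds ratio is conditional on stratum (a standardised risk difference may be added);
- the Aim 3 interactions are extensions of these models.

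If the PHS form already specifies this, a cross-reference in C5 is enough. No new data are needed. The cost is two degrees of freedom in the logistic model and four in the mixed model: about half a power point at most in the assumed 80-family trial with no prognostic effect.
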